15.5.5 PK parameters summarization

Table 8 SOBI003 PK Summary Statistics

Variable	Summarized with:
AUC_{0-168h} , C_{max} , $C_{end\ of\ inf}$, $C_{pre-dose}$, C_{trough} , CL , R_{Cmax} , $R_{Ctrough}$, $R_{AUC0-168h}$, fluctuation%	n, arithmetic mean, SD, CV%, minimum, median, maximum, geometric mean and geometric CV%
$t_{1/2}$, and λz	n, arithmetic mean, SD, CV%, minimum, median, maximum

Variable	Summarized with:
t_{max} , $t_{end\ of\ inf}$, t_{last} (actual time)	n, minimum, Q1, median, Q3 and maximum

AUC_{0-168h} = area under the serum concentration-time curve from time 0 to 168 hours after dose; $C_{end\ of\ inf}$ = observed serum concentration at the end of infusion of SOBI003; CL = clearance; C_{max} = maximum observed serum concentration; $C_{pre-dose}$ = observed serum concentration immediately before the start of infusion of SOBI003; C_{trough} = minimum observed serum concentration; CV = coefficient of variation; R_{Cmax} = C_{max} accumulation ratio; $R_{CTrough}$ = C_{trough} accumulation ratio; $R_{AUC0-168h}$ = AUC_{0-168h} accumulation ratio; SD = standard deviation; $t_{end\ of\ inf}$ = time of the end of the infusion of SOBI003; t_{last} = time of the last measurable concentration; t_{max} = time at which the maximum serum concentration is observed; $t_{1/2}$ = half-life; λz = terminal elimination rate constant.

The following conventions will be used for the presentation of the descriptive statistics of PK parameters and of serum concentrations:

Table 9 PK Reporting Precision

Statistics	Degree of Precision
Minimum, Maximum	3 significant digits or as needed based on actual measured values (for example PK concentrations)
Mean (arithmetic and geometric), Median	4 significant digits
Standard deviation	5 significant digits
CV and Geometric CV	1 decimal point

CV = coefficient of variation

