7.5.6.3 Pharmacokinetic calculations

PK calculations, based on serum concentrations, are performed in Phoenix WinNonlin by means of NCA. Results on PK parameters calculated by NCA will be available continuously during the study in order to support dose escalation decisions at SRC meetings.

Individual serum concentration data from each patient and the exact time points for blood sampling are used throughout the analyses. Samples with serum concentrations below the lower limit of quantification (LLOQ) appearing in the terminal samples will be omitted from the analysis. The following PK parameters are determined for SOBI003:

At Weeks 1, 2, 3, 4, 8, 12, 24:

- The observed serum concentration immediately before the start of infusion of SOBI003, $C_{\text{Pre-dose}}$

At Weeks 1, 2, 3, 4, 8, 12, 24:

- The time of the end of the infusion of SOBI003, $t_{\text{End of inf}}$
- The observed serum concentration at the end of infusion of SOBI003, $C_{\text{End of inf}}$

At Weeks 1, 4, 12 and 24:

- The minimum observed serum concentration, C_{Trough}
- The maximum observed serum concentration, C_{max}
- The time at which the maximum serum concentration is observed, t_{max}
- Clearance, CL
- The area under the plasma concentration-time curve from time 0 to last sample, AUC_{168h}
- The half-life, $t_{\frac{1}{2}}$

The area under the plasma concentration-time curve from time 0 to last sample, AUC_{168h} calculated according to the linear log trapezoidal method. Other PK parameters may be calculated as applicable.

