Start of infusion		X											
Stop of infusion						X							
Adverse events	X ^g	X	X	X	X	X	X	X	X	X	X	X	X
Blood sampling for:													
Safety laboratory	X											X ^h	
Immunogenicity	X ⁱ												
HS	X ^j												
PK	X ^j						X	X ^k					
Urine collection for:													
Safety laboratory (Dipstick)	X											X ^h	
HS	X ^j												

- a Only applicable at Week 1. Medical conditions present pre-infusion are recorded as medical history. At the time of the 1st infusion, the patient should not have evidence of ongoing infection, as judged by the investigator. In such case, the 1st infusion should be postponed until the infection has resolved.
- b General appearance and skin to capture any physical changes during infusion. Any new clinically significant finding or worsening of MPS IIIA related symptoms should be reported as an AE.
- c Only applicable at Week 1. Weight obtained pre-infusion at Week 1 determines the actual SOBI003 dose to be administered at Weeks 1 to 4. The dose may be adjusted in the week after the body weight is obtained, at the discretion of the investigator.
- d Only applicable at Weeks 1 and 2
- e Continuous monitoring up to 24 hours after start of infusion
- f Within 30 to 60 minutes prior to each SOBI003 infusion, a single dose of a non-sedative antihistamine should be administered.
- g SAE(s) are reported from the time point when ICF is signed until 28 days past last dose of IMP. AEs are reported from start of first SOBI003 infusion.
- h NOT applicable at Week 4 and blood sampling is not applicable at Week 3 for patients < 15 kg body weight.
- i Only applicable for Weeks 2 and 4.
- j NOT applicable for Week 1.
- k Only applicable for Weeks 1 and 4. PK sampling time points are pre-dose, 4 hours (end of infusion), 6, 12, 24, 48, 96, 120 and 168 hours after start of infusion. In case SOBI003 infusion is prolonged, applicable adjustments the PK sampling time points are applied (refer to CSP Table 6).
- l If the infusion time is reduced or extended, hourly vital signs during infusion should be recorded.

Table 3 Detailed schedule of events – Weeks 12, 16, 20 and 24; PK at Weeks 5, 8, 12, 13, 16, 20, and 24; ADA, Serum HS, and Urine HS at Weeks 8, 12, 16, 20, and 24

		Weeks 12, 16, 20 and 24														Week 12	Week 24 END
		PK: Weeks 5, 8, 12, 13, 16, 20, and 24 ADA, Serum HS, Urine HS: Weeks 8, 12, 16, 20, and 24															
Day	1	1	1	1	1	1	1	1	1	2	3	4	5	6	7 (8 ^a)	7 (8 ^a)	

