15.3 Serum PK endpoints

The following parameters will be derived:

- Serum SOBI003 PK parameters at Weeks 1, 4, 12, and 24 and as applicable at Weeks 16 and 20; $t_{end\ of\ inf}$, $C_{end\ of\ inf}$, C_{max} , t_{max} , $C_{pre-dose}$, C_{trough} , CL , AUC_{0-168h} , $t_{1/2}$

Other parameters may be derived such as accumulation ratios R_{Cmax} , $R_{Ctrough}$, $R_{AUC_{0-168h}}$, fluctuation%, etc.

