15.5 Presentation of concentration data in serum and CSF

15.5.1 Handling of missing data

Missing concentration data for all patients who are administered scheduled study treatment will be considered as non-informative missing and will not be imputed. No concentration estimates will be provided for missing sample values.

For the derivation of the area under the curve (AUC) and for the individual serum concentration versus time curves, the following rules will apply:

- Concentration values below the assay's lower limit of quantification (LLOQ) in pre-dose samples and in samples taken before the time of the 1st quantifiable concentration will be treated as zero; except for the log-transformed concentrations for graphs, where concentration values below the assay's LLOQ in pre-dose samples will be set to LLOQ/2;
- The sampling time of pre-dose samples relative to dosing will also be treated as zero;
- In case a concentration value pre-dose is not available, the concentration value collected at screening may be used for derivation of AUC;
- Post-dose below LLOQ values after the 1st quantifiable time point will be set to missing;
- Samples taken outside the sampling windows may be excluded from by-time point summary statistics; this will be determined prior to database lock.

For serum concentration summary, the following rules will apply:

- Serum concentrations below LLOQ in pre-dose samples and in samples taken before the time of the 1st quantifiable value will be set to zero;
- The serum concentrations below LLOQ after quantifiable concentration will set to missing.

For CSF concentration summary, the following rules will apply:

- CSF concentrations below LLOQ in the pre-dose samples taken before the time of the 1st quantifiable value will be set to zero;
- The CSF concentrations below LLOQ after quantifiable concentration will be summarized.

No further imputation will be applied to any missing values.

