15.5.4 PK parameters derivation

The PK parameters will be estimated as follows:

- The apparent C_{max} and the corresponding T_{max} will be read directly from the concentration-time plot (observed data).
- AUC_{last} is calculated using the log-linear trapezoidal interpolation rule for intravenous model.

Terminal elimination parameters, elimination rate constant and $t_{1/2}$, will be derived as below if sufficient data are available.

The terminal elimination rate constant (λz) will be determined by log linear regression obtained on at least the 3 last quantifiable concentrations and will not include C_{max} ;

$t_{1/2}$ is calculated by the program as $\ln 2/\lambda z$;

The AUC_{0-inf} is calculated by the program as:

$AUC_{0-inf} = AUC_{last} + AUC_{extrap}$ where last is the sampling time point of the last measurable concentration (t_{last}). AUC_{extrap} is calculated by the program as: $C_{last}/\lambda z$, where C_{last} is the observed concentration at time t_{last} and λz is the elimination rate constant during the apparent terminal elimination phase; AUC_{0-inf} will only be presented for patients with a reliable λz ;

For single-dose, CL is calculated by program as (dose/ AUC_{0-inf}) and for multiple-dose, CL is calculated by program as (dose/ AUC_{0-168h});

V is calculated by the program as (dose/ AUC_{0-inf})/ λz ;

Fluctuation % is calculated by the program as $100 \times ((C_{max} - C_{min})/C_{avg})$.

The following PK acceptance criteria will be considered to when the reliability of elimination parameters are assessed:

- Number of points to calculate λz is greater than or equal to 3 excluding C_{max} point;
- Interval for calculation of λz is longer than half-life;
- The adjusted square of the correlation coefficient (Rsquare adjusted) for the goodness of fit of the regression line through the data points must be ≥ 0.75 ;
- $AUC_{extrap} \leq 30\%$.

However, less strict acceptance criteria may be applied, in exceptional cases, since the number of PK samples are limited. PK parameters may be calculated and reported even if the strict criteria are not fulfilled. When PK parameters are based on less strict criteria, this will be described on an individual level.

Accumulation ratios will be calculated as ratio of PK parameters (C_{max} , C_{min} , $C_{End\ of\ inf}$, AUC_{0-168h}) for the last vs 1st dose.

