15.6 Attainment of steady state for SOBI003

Aggregate assessment of trough concentrations by repeated measures analysis of variance (ANOVA) may be used to evaluate attainment of steady state and determine the dose number to achieve steady state for SOBI003 (11). The approach is based on the comparison of log-transformed trough concentration values for each dose to the mean of the results for all the following doses.

If data are sufficient to support the analysis, repeated measures analysis will be carried out on log-transformed C_{trough} (pre-infusion concentrations) for Week 2 through Week 24 for each infusion where data available. The following SAS code will be used to conduct the repeated measurement analysis:

```

PROC MIXED
  CLASS dose patient;
  MODEL logCmin = dose;
  REPEATED / TYPE=UN SUBJECT=patient;
  RUN;

```

The trough concentrations observed after Week 2 through Week 24 for SOBI003 for each infusion will be compared with the average trough levels for the rest of the period to determine the time at which steady state was achieved. Contrasts will be tested between a time point and the pooled mean over all remaining time points, such as:

Week 2 pre-infusion value vs. the average of Weeks 2 through 24

Week 3 pre-infusion value vs. the average of Weeks 4 through 24

...

Week 8 pre-infusion value vs. the average of Weeks 12 and 24

Week 12 pre-infusion value vs. the Week 24

The first non-significant comparison will be concluded to be the dosing interval at which steady state concentrations are attained. The p-value for difference of least square means (LSM), LSM ratio, and the 90% confidence interval (CI) for the contrasts will be provided.

Additionally, steady state will be assessed using a mixed model (12) with repeated measures performed on C_{min} ss including dosing interval (Week 2 through Week 24 for SOBI003) as a covariate and subject as a random effect. A random slope effect for dosing interval will also be included. The linear effect of dosing interval on the C_{min} ss over time will be used to assess the assumption of steady state.

```
PROC MIXED data=cminDATASET;
  CLASS subject ;
  MODEL log_Cmin_ss = doseno / ddfm=kr;
  RANDOM intercept doseno /subject= subject;
  RUN;
```

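### Ctrough has conflicting definitions, and under the minimum-observed rule the Week 24 to Week 1 trough ratio does not compare like with like

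*SAP*

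**What the plan says.** **Definition.** Protocol 7.5.6.3 lists Ctrough at Weeks 1, 4, 12 and 24 as "The minimum observed serum concentration", alongside a separate C_Pre-dose. The footnote to SAP Table 8 repeats this: "minimum observed serum concentration; CV = coefficient of variation" (the words after the semicolon belong to the next abbreviation). SAP 15.6 instead explains Ctrough as "pre-infusion concentrations) for Week 2 through Week 24 for each infusion where data available" and calls the variable Cmin in its code.

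**Ratio.** SAP 15.5.4 states: "Accumulation ratios will be calculated as ratio of PK parameters", names Cmax, Cmin, C_End of inf and AUC0-168h, and takes them "for the last vs 1st dose". Cmin is not defined. Table 8 reports the result as R_Ctrough. SAP 15.3 is more tentative: "Other parameters may be derived such as accumulation ratios".

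**Samples.** In SAP Table 7 the Week 1 profile starts at 4 h and ends at 168 h. Weeks 4, 12 and 24 have both a pre-infusion and a 168 h sample in every weight band. In the lowest band (10 to <15 kg in protocol Table 6), Week 1 has only the 4 h and 168 h samples.

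**A Week 1 pre-dose value.** Footnote j to SAP Table 2 (section 4.1) marks the pre-infusion PK sample "NOT applicable for Week 1". Footnote k to the same table lists pre-dose among the Week 1 and Week 4 times, and protocol 7.5.6.3 includes Week 1 for C_Pre-dose.

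**LLOQ and endogenous enzyme.** Under SAP 15.5.1, values below LLOQ "in pre-dose samples and in samples taken before the time of the 1st quantifiable concentration will be treated as zero", and later post-dose ones become missing. These rules are written for AUC, individual curves and concentration summaries; Ctrough is not mentioned. Protocol 7.5.6.3 leaves out terminal samples below LLOQ. Protocol 7.5.6.2 warns that the assay may detect endogenous enzyme and offers subtraction only as an example of how to handle it.

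**The concern.** One symbol covers three possible quantities, so two programmers could produce different Ctrough tables from the same data. Under the definition given twice, the set of samples that feeds the minimum changes between the first and the last dose, and the ratio compares exactly those two. An apparent fall from Week 1 to Week 24 could then come from the definition alone.

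This matters because protocol 7.5.5.3 intends to explore the effect of anti-drug antibodies on PK, and a falling trough is one sign of such an effect. SAP 4.1 leaves six patients in two cohorts of three, so each patient's value carries weight.

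**Working it through.** The documents state no accumulation ratio, so there is no figure to reproduce. Within-patient CV, half-life, LLOQ and the endogenous fraction are not given; they are assumed below and shown as ranges.

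**1. Week 1 minimum is the 168 h value; Week 24 minimum covers both troughs.** Protocol 7.2 expects steady state to be approached by about four weeks, so the two Week 24 troughs have about the same expected value. For two independent log-normal values with log-SD s, the mean log of the smaller lies s/√π below the common mean. The ratio is therefore multiplied by exp(−s/√π), with s = √ln(1 + CV²).

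| CV | s | exp(−s/√π) | Bias |
|---|---|---|---|
| 10% | 0.100 | 0.945 | −5.5% |
| 20% | 0.198 | 0.894 | −10.6% |
| 30% | 0.294 | 0.847 | −15.3% |
| 50% | 0.472 | 0.766 | −23.4% |

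A one-compartment simulation checks this. It used 3% of the dose in hour 1 and 97% over the next 3 h, 24 weekly doses, the full Table 7 post-dose times and 100,000 replicates. At half-lives of 7.5 h and 24 h the bias was about −5.5%, −10.5%, −15% and −23% for the four CVs. At a half-life of 168 h it shrank to −5.0%, −7.4%, −7.9% and −8.5%. In that case other late samples lie close to the 168 h value, so the Week 1 minimum is also pulled down.

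**2. A Week 1 pre-dose value is counted and is zero.** This arises if it is below LLOQ and set to zero, or if endogenous signal is subtracted to zero. The denominator is 0, so neither R_Ctrough nor its geometric mean in Table 8 exists.

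**3. A Week 1 pre-dose value is counted, is quantifiable and is not corrected.** Let the endogenous level be a fraction f of the Week 1 168 h drug level. The Week 1 minimum is then the endogenous level, and the reported ratio is (true ratio)/f + 1. The true ratio is about 1/(1 − 2^(−168/t½)): 1.008 at 24 h and 2.0 at 168 h.

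| f | Reported, t½ 24 h (true 1.008) | Reported, t½ 168 h (true 2.0) |
|---|---|---|
| 0.05 | 21.2 | 41 |
| 0.20 | 6.0 | 11 |
| 0.50 | 3.0 | 5 |

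**4. The 168 h value is below LLOQ and left out.** In the lowest weight band the only on-treatment Week 1 sample remaining is the end-of-infusion one, so the reported trough is close to a peak. This could happen. Protocol 5.1.3 predicts Cmax,ss 0.89 µmol/L and AUC 11.5 h·µmol/L at 3 mg/kg. For a one-compartment model with a constant 4 h infusion, (1 − e^(−4k))/4 = 0.89/11.5 = 0.0774, which gives a half-life of about 7.5 h. The 168 h concentration is then 0.89·e^(−164k) ≈ 2 × 10⁻⁷ µmol/L. With the stepped infusion the half-life is about 7.8 h and the concentration about 4 × 10⁻⁷. A slower terminal phase would give higher values; the documents do not settle this.

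**5. The same sampling time in both terms.** With 168 h over 168 h, the simulated geometric mean ratio was 1.00, 1.10, 1.33 and 2.00 at half-lives of 7.5, 48, 84 and 168 h, against true values of 1.000, 1.097, 1.333 and 2.000.

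**The case against.** A reader might infer that R_Ctrough simply is biased low or undefined. The documents do not support that as a flat statement. Nowhere do they say that the minimum runs over both the pre-infusion and the 168 h sample. Since C_Pre-dose is its own parameter, Ctrough could be read as the minimum after the dose, normally the 168 h value in every profile week. On the SAP 15.6 reading, the Week 2 pre-infusion sample serves as the dose-1 trough, and Table 7 labels that sample both ways. The zero denominator needs a Week 1 pre-dose sample that Table 7 does not schedule, plus an LLOQ rule not written for Ctrough. The direction is not fixed either, as step 3 shows.

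The size is also modest. In step 1, with three patients per cohort, the bias in the mean log ratio is s/√π = 0.564s. Its standard error is s·√((2 − 1/π)/3) = 0.749s, so the bias is about 0.75 standard errors whatever s is, and relatively less once patients truly differ. Loss of exposure would also be visible in the Cmax, C_End of inf and AUC0-168h ratios, the individual trough plots (SAP 15.5.2) and the SAP 15.6 trough analysis.

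These points limit the claim without removing it. The charitable readings have to be supplied by the reader, while the literal definition is written in both documents. The SAP 15.6 reading would make Ctrough duplicate C_Pre-dose, and the Week 24 pre-infusion value belongs to dose 23, not to the last dose.

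**Conclusion.** The inconsistency is real and should be resolved before the PK tables are programmed. What the documents establish is that a named secondary endpoint has conflicting definitions, and that the literal one yields a different quantity at Week 1 than at Week 24.

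The effect on the ratio is conditional. It is low by about 5% to 23% for an assumed CV of 10% to 50%, and by 5% to 8.5% over the same CVs at a 168 h half-life. It is undefined if a zero Week 1 pre-dose value is counted, and inflated, possibly several-fold, if an uncorrected endogenous value is counted. Which case applies depends on the conflicting footnotes about a Week 1 pre-dose sample and on LLOQ and endogenous-signal rules that are not stated for Ctrough.

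It would go too far to infer that a loss of exposure will be wrongly reported. Only Week 24 against Week 1 enters the ratio, the ratio is descriptive in six patients, and other outputs address the same question. The primary safety endpoint is not touched.

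**What to change.** In SAP 15.3, 15.5.4, 15.5.5 and 15.6:

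- Define Ctrough as the concentration at the end of the dosing interval, 168 h after the start of infusion and before the next dose. Replace Cmin by Ctrough wherever trough is meant; if Cmin is kept for the fluctuation formula, define it there.
- Compute R_Ctrough as the Week 24 168 h value over the Week 1 168 h value.
- Keep C_Pre-dose as a separate parameter, and exclude the pre-treatment sample from Ctrough.
- Report a 168 h value below LLOQ as below LLOQ and do not calculate the ratio, rather than substituting an earlier sample.
- Apply the same endogenous-baseline correction to both terms.
- Reconcile the footnotes on a Week 1 pre-dose PK sample.

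The cost is a few lines of SAP text. Table 7 already schedules the 168 h sample in every weight band at Weeks 1, 4, 12 and 24, so no new blood is drawn. The one loss is that patients with a 168 h value below LLOQ at either week will have no ratio, so Table 8 should show how many contribute.

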15.6 Attainment of steady state for SOBI003

Aggregate assessment of trough concentrations by repeated measures analysis of variance (ANOVA) may be used to evaluate attainment of steady state and determine the dose number to achieve steady state for SOBI003 (11). The approach is based on the comparison of log-transformed trough concentration values for each dose to the mean of the results for all the following doses.

If data are sufficient to support the analysis, repeated measures analysis will be carried out on log-transformed C_{trough} (pre-infusion concentrations) for Week 2 through Week 24 for each infusion where data available. The following SAS code will be used to conduct the repeated measurement analysis:

```

PROC MIXED
  CLASS dose patient;
  MODEL logCmin = dose;
  REPEATED / TYPE=UN SUBJECT=patient;
  RUN;

```

The trough concentrations observed after Week 2 through Week 24 for SOBI003 for each infusion will be compared with the average trough levels for the rest of the period to determine the time at which steady state was achieved. Contrasts will be tested between a time point and the pooled mean over all remaining time points, such as:

Week 2 pre-infusion value vs. the average of Weeks 2 through 24

Week 3 pre-infusion value vs. the average of Weeks 4 through 24

...

Week 8 pre-infusion value vs. the average of Weeks 12 and 24

Week 12 pre-infusion value vs. the Week 24

The first non-significant comparison will be concluded to be the dosing interval at which steady state concentrations are attained. The p-value for difference of least square means (LSM), LSM ratio, and the 90% confidence interval (CI) for the contrasts will be provided.

Additionally, steady state will be assessed using a mixed model (12) with repeated measures performed on C_{min} ss including dosing interval (Week 2 through Week 24 for SOBI003) as a covariate and subject as a random effect. A random slope effect for dosing interval will also be included. The linear effect of dosing interval on the C_{min} ss over time will be used to assess the assumption of steady state.

```
PROC MIXED data=cminDATASET;
  CLASS subject ;
  MODEL log_Cmin_ss = doseno / ddfm=kr;
  RANDOM intercept doseno /subject= subject;
  RUN;
```

The DDFM = KR (KenwardRoger) option performs the degrees-of-freedom calculations detailed by Kenward and Roger (1997) (13). As recommended, the denominator degrees of freedom for the fixed effects will be estimated as the most appropriate method in the mixed-model analysis.

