4.1 Overall study design and plan

This is an open-label, non-controlled, parallel, sequential ascending multiple-dose, multicenter study to assess the dose related safety, tolerability, pharmacokinetics (PK), and pharmacodynamics (PD) of SOBI003 in pediatric MPS IIIA patients. An overview for the study design is presented in [Figure 1](#).

In February 2020, Sobi decided to discontinue the SOBI003 program. At the time of the decision, 3 patients had been included in Cohort 1 and 3 patients in Cohort 2 of the FIH study (SOBI003-001). All patients had been enrolled in the Extension study (SOBI00-002) and will have the possibility to continue their treatment for a total of two years. Thus, Cohort 3 in the FIH study (SOBI003-001) will not be started. Statistical analysis for the FIH study (SOBI003-001) CSR will be done for Cohort 1 and 2.

Figure 1 Overview for study design for Study SOBI003-001

SOBI003 is administered as weekly intravenous (i.v.) infusions over a period of time of 4 hours. The study treatment period comprises 24 weekly infusions. Prior to initiation of each infusion, the patients are pre-treated with a single dose of non-sedative antihistamine. If infusion-related reactions occur, then the infusion duration may be expanded up to 24 hours and supportive medication may be administered, at the discretion of the investigator.

The study is planned to consist of 3 dose cohorts, each comprising 3 patients, provided that no significant safety concern arise. An additional cohort comprising 3 patients may be added, if deemed necessary to more accurately characterize the safety, tolerability, PK or PD.

The screening visit can be performed up to 12 weeks prior to the first SOBI003 infusion. At the screening visit, the MPS IIIA diagnosis is verified and the genotype is determined at a central laboratory. Patients are assigned to a dose cohort in consecutive order as the eligibility criteria have been confirmed, with prioritization of the younger patients.

Treatment initiations will be staggered within each cohort in order to be able to observe, interpret and treat possible adverse reactions and to ensure that such reactions can be dealt with promptly. For each cohort, safety review committee (SRC) meetings are scheduled approximately 3 weeks after completion of the 3rd patient's 4th dose administration. Based on the safety, immunogenicity, PK and PD data, the SRC will determine what dose to apply in the next cohort.

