- h PK sampling time points are 4 hours (end of infusion), 6, 12, 24, 48, 96, 120 and 168 hours after start of infusion. Samples are also collected at 4 hours (end of infusion) and at 168 hours (Day 8) at Week 5, 8, 12, 13, 16, 20 and 24. The 168-hour sample at Week 12, 16, and 20 is thus taken prior to start of infusion on Day 1 of Week 13, 17, and 21, respectively. The 168-hour sample at Week 24 is thus taken on Day 8 (For patients continuing in the extension study (SOBI003-002), this is prior to start of infusion on Day 1 of the extension study).
- i In case both BSID-III and KABC-II are to be administered, there should be at least 2 days between the assessments (i.e., one should then be administered on Days 4 or 5 of Week 24 and the other one on Day 7 of Week 24). A +7-day window is applied for the BSID III/KABC-II assessments.
- j CSHQ is completed any time during the infusion days
- k Weight is obtained prior to preparation of the SOBI003 infusions solution at Week 12. The weight is obtained either the day prior to the infusion or the day of infusion. The dose may be adjusted on the week after the body weight is obtained, at the discretion of the investigator.
- l At each infusion, vital sign assessments are done pre-infusion, mid-infusion and within 1 hour after end of infusion. Timing of assessment to be adjusted in accordance with infusion time.
- m Only applicable for Week 12 and 24.

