15.2 Serum PK sampling schedule

Table 7 Detailed PK blood sampling schedule

Week	Time	BW \geq 20 kg No of samples ^a	BW \geq 15 kg No of samples ^a	BW \geq 10 kg No of samples ^a
	Screening	1	1	1
	Baseline	1	1	1
Week 1	4h / End of Infusion	2	2	2 ^c
	6h	2		
	12h	2		
	24h	2	2	
	48h	1		
	72h^b	1	1	
	96h^b	1	1	
	120h	1	1	
Week 1 (2)	168h/Pre-infusion	1	1	1
	4h / End of Infusion	2	2	
Week 3	Pre-infusion	1	1	
	4h / End of Infusion	2	2	
Week 4	Pre-infusion	1	1	1
	4h / End of Infusion	2	2	2
	6h	2	2	
	12h	2	2	
	24h	2	2	2
	48h	1	1	
	72h^b	1	1	1
	96h^b	1	1	1
	120h	1	1	
Week 4 (5)	168h/ Pre-infusion	1	1	1
Week 8	Pre-infusion	1	1	1
	4h / End of Infusion	2	2	2
Week 12	Pre-infusion	1	1	1
	4h / End of Infusion	2	2	2
	6h	2	2	
	12h	2	2	
	24h	2	2	2
	48h	1	1	

Week	Time	BW \geq 20 kg No of samples ^a	BW \geq 15 kg No of samples ^a	BW \geq 10 kg No of samples ^a
	72h^b	1	1	1
	96h^b	1	1	1
	120h	1	1	
	168h	1	1	1
Week 16	Pre-infusion	1	1	1
	4h / End of Infusion	1	1	1
	168h	1	1	1
Week 20	Pre-infusion	1	1	1
	4h / End of Infusion	1	1	1
	168h	1	1	1
Week 24	Pre-infusion	1	1	1
	4h / End of Infusion	2	2	2
	6h	2	2	
	12h	2	2	
	24h	2	2	2
	48h	1	1	
	72h^b	1	1	1
	96h^b	1	1	1
	120h	1	1	
	168h	1	1	1

a If Number = 1; PK blood sample is collected from central venous access port. If Number =2; One PK sample will be collected from the central venous access port and one PK sample will be collected from a peripheral venous line. At the Screening visit 1; from peripheral venous line as no central access port has yet been placed.

b If infusion is prolonged, PK samples will be collected 2h and 8h after End of infusion. Thereafter PK sampling will be conducted according to ordinary PK sampling schedule (refer to CSP Section 7.5.6.1).

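### With 6 patients, the unstructured covariance that SAP 15.6 specifies for the week-by-week steady-state contrasts cannot be estimated

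*SAP*

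**What the plan says.** SAP 15.6 opens by saying that a repeated-measures ANOVA may be used to judge steady state. It continues: "If data are sufficient to support the analysis, repeated measures analysis will be carried out on log-transformed" trough, "for Week 2 through Week 24 for each infusion where data available". It then commits to printed SAS code, whose key lines are "MODEL logCmin = dose" and "REPEATED / TYPE=UN SUBJECT=patient". Each week's trough is contrasted with the mean of later troughs, and the earliest contrast that is not significant is taken as the interval at which steady state is reached. Table 14.3.4.9.3 in the SAP's output index is reserved for the result.

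On the data available, SAP 4.1 states that "3 patients had been included in Cohort 1 and 3 patients in Cohort 2 of the FIH study" and that Cohort 3 will not start.

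15.6 also plans a second model: log trough regressed on dose number, with random intercept and slope per patient and Kenward-Roger degrees of freedom. SAP 17 withdraws the heparan sulfate mixed models because the programme was discontinued, but leaves 15.6 unchanged.

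**The concern.** An unstructured covariance gives every trough its own variance and every pair of troughs its own covariance. That needs more patients than troughs, and here the troughs equal or outnumber the patients on every reading of the schedule.

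The decision rule makes this matter. Steady state is declared at the first contrast that fails to reach significance, so the answer moves with the standard errors: too large and steady state is declared early, too small and it is declared late. A covariance fit with no proper maximum does not supply standard errors that can carry that rule. The patient count stands in the same SAP, so the shortfall is already known and need not wait for the data.

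**Working it through.** The documents give no parameter count, power or sample size for this analysis, so there is no figure of the plan's to reproduce.

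**Inputs**
- Patients: n = 6, in two dose levels of 3 (SAP 4.1).
- Fixed effects: one mean per trough. The class variable `dose` is not defined. I read it as dose number, because as dose level the model would have no time effect and the week contrasts could not be formed.
- Troughs from Week 2 to Week 24, p:
  - Contrast list in 15.6: Weeks 2, 3, 4, 8, 12, 24, so p = 6, or 7 with Week 5.
  - Protocol Table 6, 15 kg and above: Weeks 2, 3, 4, 5, 8, 12, 13, 24, so p = 8.
  - SAP Table 7, 15 kg and above: those eight plus Weeks 16, 17, 20 and 21, so p = 12. Weeks 13, 17 and 21 count because "The 168-hour sample at Week 12, 16, and 20 is thus taken prior to start of infusion on Day 1 of Week 13, 17" (SAP Table 3, note h, which pairs the Week 20 sample with Week 21 in the same way).

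**Step 1: parameters against data.** Covariance parameters = p(p+1)/2; means = p; maximum observations = 6p.

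| p | Covariance parameters | Means | Total | Observations |
|---|---|---|---|---|
| 6 | 21 | 6 | 27 | 36 |
| 7 | 28 | 7 | 35 | 42 |
| 8 | 36 | 8 | 44 | 48 |
| 12 | 78 | 12 | 90 | 72 |

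The raw count exposes the problem only at p = 12. For the others the rank decides.

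**Step 2: rank.** After p means are removed, n patients leave a residual cross-product matrix of rank at most n − 1 = 5. A positive-definite unstructured estimate needs n ≥ p + 1: 7 patients for 6 troughs, 8 for 7, 9 for 8 and 13 for 12. Six patients meet none of these. If the model is fitted within dose level, as SAP 7 suggests for PK, the rank is 3 − 1 = 2.

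**Step 3: what the likelihood does.** There are p − 5 directions without residual variation. As the fitted variance e in those directions shrinks, the REML log-likelihood gains (n − 1)/2 × ln(1/e) in each. Moving e from 1e-1 to 1e-8 adds 2.5 × 7 × ln 10 = 40.3 per direction: 40.3 at p = 6, 120.9 at p = 8 and 282.1 at p = 12. Simulated data agree to rounding (−5.6 to 34.7, 0.2 to 121.0 and 9.8 to 291.9). The likelihood has no maximum. At p = 5 it stays flat at −9.0.

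**Step 4: row order.** The `REPEATED` statement names no effect, so rows are placed by order within patient. The Week 3 entry in SAP Table 7 reads "Week 3 Pre-infusion 1 1", with nothing in the lowest weight column. If a patient under 15 kg has no Week 3 row, position 2 of that patient's covariance holds Week 4, and so on to position 11, which holds Week 24 instead of Week 21.

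**The case against.** The strongest reply is that the model is optional and conditional, and that 15.6 supplies another one. Both are true in part. A reader might infer that the steady-state assessment is lost, or that its model must be chosen after seeing the data. The documents do not support that: the random-slope model is pre-specified, needs few variance components and names dose number explicitly, and trough plots and summaries are also planned. But that model tests a linear trend. It does not say at which dose steady state begins, which is the purpose of the contrasts. Nor does the condition help while sufficiency is undefined. Missing values would rescue the unstructured fit only if whole weeks dropped out until 5 or fewer remained.

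Three other strong readings go too far.
- **Every contrast is invalid.** With complete data each contrast is a mean of within-patient differences and could be tested on 5 degrees of freedom. What fails is the specified fit; the SAP does not plan the paired version. No SAS run shows how the software would behave.
- **Pooling 3 and 10 mg/kg distorts the contrasts.** If troughs are dose-proportional the offset is ln(10/3) = 1.2, but a constant offset cancels within patient when data are complete. Pooling is itself unsettled, since SAP 7 says PK is analysed by dose level.
- **Weeks are misaligned.** This needs a patient under 15 kg whose Week 3 row is absent and not kept with a missing response. The documents give neither the six weights nor the data layout. It would distort the covariance and standard errors, not the week means.

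**Conclusion.** The point stands for the covariance specification. On the trough lists of 6, 7, 8 or 12, the unstructured matrix in 15.6 exceeds what 6 patients can support (rank 5, or 2 per dose level), so the contrasts behind Table 14.3.4.9.3 have no proper fit as coded. This assumes that `dose` means dose number and that at least 6 distinct weeks contribute troughs. The one boundary case is the shortest list with Week 3 missing in all six patients, which leaves 6 − 1 = 5 troughs and a fit that is just possible.

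The consequence is limited. This is a secondary PK analysis and does not touch the primary safety endpoint. It should still be corrected, because the failure can be seen now and the repair is small.

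**What to change.** Replace the first block of code in SAP 15.6 with:

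`CLASS patient week; MODEL logCtrough = week / DDFM=KR; REPEATED week / TYPE=CS SUBJECT=patient;`

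A random patient effect would serve in place of the `REPEATED` line. Add cohort as an optional fixed effect if the two dose levels are fitted together. State what counts as sufficient data, and make the change before database lock.

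This uses 2 covariance parameters in place of 36 (p = 8) or 78 (p = 12). It leaves 48 − 8 = 40 or 72 − 12 = 60 observations after the means, less one for each patient under 15 kg. Naming week also removes any dependence on row order.

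The cost is a few lines of code and no new data. The downside is that equal variance across weeks and equal within-patient correlation are assumed, and 6 patients cannot test either.
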